4.3.3 Follow-up for Withdrawn Participants

Outreach will be made to ensure that participants who are withdrawn, or who withdraw from the study, during the active observation or follow-up period will complete all safety and available assessments for the Early Withdrawal Visit as outlined in this protocol. The investigator should inform the participant that these assessments are for their own well-being and, if possible, for study purposes. Additional information regarding ongoing AEs may be provided as a follow-up report.

4.3.4 Documentation of Withdrawal/Discontinuation

Reasons for withdrawal of individual participants from the study prior to final protocol required visit and/or final safety follow-up are to be recorded on the eCRF. The reason for withdrawal from the study will be recorded as one of the following:

- Lost to Follow-up (**Note:** Requires documentation of at least three unsuccessful attempts to contact participants, lost to follow-up will be determined after the date of the participant's projected last visit)
- Adverse event
- Pregnancy
- Protocol deviation (that results in discontinuation)
- Noncompliance to IP
- Physician (ie, investigator) decision
- Other

Safety follow-up for AEs should occur for all participants, for information on safety followup for withdrawn participants see Section 4.3.3.

4.3.5 Participant Replacement

Participants who undergo Early Discontinuation or withdrawal of consent after randomization and before receiving treatment may be replaced at the sponsor's discretion. Participants who undergo Early Discontinuation after vaccination will not be replaced.

5 TREATMENT OF PARTICIPANTS

5.1 Investigational Products

5.1.1 PXVX0317 Vaccine

The PXVX0317 vaccine is comprised of CHIKV VLP adsorbed on aluminum hydroxide adjuvant 2%, and formulation buffer supplied as a single dose in a pre-filled glass syringe. CHIKV VLP refers to the VLP component of PXVX0317 produced by transient transfection of human embryonic kidney (HEK293) cells with a deoxyribonucleic acid expression plasmid encoding capsid (C) and envelope (E) E3, E2, 6K, and E1 proteins. After expression of the plasmid-encoded proteins, VLPs self-assemble and are released into the cell culture medium as ~70 nm particles. The 6K and E3 proteins have not been specifically detected in the VLPs. No replication-capable viral genetic material is incorporated into the VLPs. Virus-like particles are then concentrated from the cell supernatant purified, and buffer exchanged. The VLPs are then formulated with excipients and aluminum hydroxide adjuvant, mixed, and

filled into 1 mL glass syringes with a 0.8 mL deliverable volume. The glass syringe is sealed with a rubber closure and plastic cap. The rubber closure does not contain natural latex.

Placebo (formulation buffer) is supplied as a single dose of 0.8 mL in a pre-filled syringe.

See the pharmacy manual and the IB for additional information, including composition of PXVX0317 vaccine.

5.1.2 Placebo Pre-filled Syringe

The placebo is a sterile aqueous solution with the same excipient composition as the drug product without CHIKV VLP and aluminum hydroxide adjuvant. The placebo is filled into 1 mL glass syringes with a 0.8 mL deliverable volume. The placebo is stored at 2.0 to 8.0°C. The glass syringe is sealed with a rubber closure and plastic cap. The rubber closure does not contain natural latex.

See the pharmacy manual for additional information, including composition of the placebo.

5.1.3 Labeling

Investigational product (PXVX0317 vaccine and placebo) will be shipped in carton kits containing labelled pre-filled syringes. Kits and syringes will be labelled with the following information:

- "Caution: New Drug Limited by Federal Law to Investigational Use Only"
- Investigational product name PXVX0317 vaccine or placebo (to maintain the blind both names will be included)
- Dose volume and container single dose of 0.8 mL in a pre-filled syringe
- Route of administration Intramuscular
- Randomization kit number (in lieu of lot numbers and manufacture date and/or expiry date to maintain the blind)
- Protocol number EBSI-CV-317-004
- Recommended storage temperature/conditions stored refrigerated at 2.0 to 8.0°C
- Sponsor Emergent Travel Health Inc.

5.1.4 Investigational Product Shipment

Investigational product will be shipped to the site at a temperature of 2.0 to 8.0°C. During shipment, the temperature of the IP will be monitored to ensure the required temperature conditions are maintained. The principal investigator (or designee) will be responsible for checking the number of syringes and the condition of the syringes received, and entering this information into the drug accountability records, and reporting the condition of shipment to

the sponsor and drug depot. Investigational product received in good condition will be automatically released for use upon confirmation of receipt as such within the RTSM system; shipments received with any excursions/issues will be placed under quarantine by the site and released for use by the sponsor following investigation. For additional information on IP shipments please refer to the study pharmacy manual.

5.1.5 Storage Conditions

Investigational product (PXVX0317 vaccine and placebo) must be stored refrigerated at 2.0 to 8.0°C in a secured area until used. The temperature in the storage area must be monitored with properly calibrated instruments and recorded on a temperature log. Any excursions must be promptly reported to the sponsor via the RTSM system; product should be quarantined by the site and may be released for use by the sponsor only after investigation and confirmation of continued stability. Please refer to the pharmacy manual for additional details.

5.1.6 Preparation

Investigational product (PXVX0317 vaccine and placebo) will be supplied as a single dose of 0.8 mL in a pre-filled syringe shipped in kits. See Section 3.3.8 for more details.

5.1.7 Drug Accountability

The investigator is responsible for maintaining accurate inventory records of IP. The investigator (or designee) will inventory all IP shipments upon receipt. The investigator must ensure that all drug supplies are kept in a secure location in the site pharmacy in accordance with recommended storage conditions (Section 5.1.5). Inventory and ongoing record of test material supplies will be documented using the electronic drug accountability form provided within the clinical trial material tracking module of the sponsor's RTSM system. These records will be reviewed by representatives of the sponsor and may be reviewed by regulatory agencies.

5.2 Study Procedures and Assessments by Visit

The timing of the study procedures and assessment below are shown in the Schedule of Events and a description of each procedure and assessment is described in Section 3.3.

5.2.1 Screening (Visit 1, within 30 days of Day 1)

Eligible participants will first undergo informed consent counseling. Once informed consent has been obtained, participants will undergo a Screening Visit to ascertain their eligibility in this study within 30 days prior to Day 1. The Screening Visit assessments will include:

- Informed consent (and informed assent, as applicable) (Section 11.1).
- Review of eligibility criteria (Section 3.3.1, Section 4.1, Section 4.2).

- Medical history (including presence of joint pain) (Section 3.3.2).
- Demographics (date of birth, race, ethnicity, and sex of participant) (Section 3.3.2).
- Prior and current medications (Section 3.3.2, Section 5.3).
- Vital signs (blood pressure, heart rate, respiratory rate, and temperature) as well as height and body weight (for BMI calculation) (Section 3.3.4).
- Complete physical exam (general appearance, eyes-ears-nose-throat, head-neck, lungs-chest, heart, abdomen, musculoskeletal, lymph nodes, skin, extremities, and neurological assessment) (Section 3.3.3).
- Blood collection for laboratory viral marker testing (HBsAg, HCV antibody [if HCV antibody is positive, HCV RNA testing can be performed], HIV-1/HIV-2) (Section 3.3.5).
- For women of CBP: blood sample for serum pregnancy test (Section 3.3.5, Section 3.3.7).
- For postmenopausal women: blood sample for FSH levels (Section 3.3.5, Section 3.3.7).
- Urine sample for toxicology (per investigator's [or designee] discretion) (Section 3.3.5).

5.2.1.1 Rescreening

Rescreening may occur given the following circumstances:

- If the participant has an acute febrile illness at the time of their scheduled enrollment, they may be re-screened 14 days after resolution of their acute illness.
- If the participant is asymptomatic but tests positive by reverse transcription polymerase chain reaction (RT-PCR) for severe acute respiratory syndrome coronavirus 2 (SARS-CoV-2) they may be rescreened provided 14 days have elapsed since the participant tested RT-PCR positive for SARS-CoV-2, the participant continues to be asymptomatic, and the participant is otherwise eligible for enrollment.
- Participants who have received licensed vaccines within 30 days of anticipated Day 1 may be rescreened provided no additional doses are anticipated up to Day 22.
- Participants who have received blood products or investigational products from participation in another clinical study may be rescreened after the appropriate duration has passed (90 days for blood products; 30 days for investigational drugs; six months prior to Screening Visit for systemic immunomodulatory or immunosuppressive medications).
- Eligible participants who are not able to be vaccinated with IP within 30 days of their screening period may be rescreened.

Rescreened participants must undergo all screening procedures again, including reconsenting and use of the same participant ID number. Participants may be rescreened one time only. Rescreening is not otherwise permitted.

5.2.2 Day 1 (Baseline, Randomization, and Administration of IP) Visit 2

The following will take place during the visit and prior to IP administration:

- Reverification of eligibility criteria.
- Review medical history.
- Review prior and concomitant medications.
- Vital signs.
- Directed physical exam (as needed, if indicated by medical history).
- For women of CBP: urine pregnancy test.
- Blood collection for anti-CHIKV SNA (Section 3.3.6, Section 6.1).
- Randomization (Section 3.4.1).
- IP administration (Section 3.3.8, Section 5.1).

The following will take place during the visit and after IP administration:

- In-clinic acute observation (Section 3.3.9).
- Vital signs.
- E-diary device, digital thermometer, and ruler distribution, set-up, and training (Section 3.3.10).
- Solicited AE, unsolicited AE, MAAE, SAE, and AESI (Sections 3.3.10 3.3.12, Section 7) evaluation.
- Record any medications that were given to participants after IP administration.

5.2.3 Day 8 (-1/+3) Visit 3

- Review e-diary.
- Solicited AE, unsolicited AE, MAAE, SAE, and AESI evaluation.
- Review concomitant medications.
- Blood collection for anti-CHIKV SNA.
- Directed physical exam (as needed).

5.2.4 Day 15 (-1/+3) Visit 4

- Unsolicited AE, MAAE, SAE, and AESI evaluation.
- Review concomitant medications.
- Blood collection for anti-CHIKV SNA.
- Directed physical exam (as needed).

5.2.5 Day 22 (-1/+3) Visit 5

- Unsolicited AE, MAAE, SAE, and AESI evaluation.
- Review concomitant medications.
- Blood collection for anti-CHIKV SNA.
- Directed physical exam (as needed).

5.2.6 Day 29 (±1) Telephone Contact for Visit 6

- Unsolicited AE, MAAE, SAE, and AESI evaluation.
- Review concomitant medications.

5.2.7 Day 92 (±3) Telephone Contact for Visit 7

- SAE, AESI, and MAAE evaluation.
- Review concomitant medications (only if associated with SAE/AESI/MAAE).

5.2.8 Day 183 (-14/+7) Visit 8 End of Study

- SAE, AESI, and MAAE evaluation.
- Review concomitant medications (only if associated with SAE/AESI/MAAE).
- Directed physical exam (as needed).
- Blood collection for anti-CHIKV SNA.

5.2.9 Early Discontinuation/Withdrawal Visit

If the Early Discontinuation/Withdrawal Visit occurs: i) within 7 days after IP administration, the Visit 3 schedule will be followed; ii) from 7 days through 21 days after IP administration, the Visit 5 schedule will be followed and; iii) after Day 22, the Visit 8 schedule will be followed.

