3.3.11 Unsolicited Adverse Events

Unsolicited AEs (AEs not listed in the e-diary) will be collected from Day 1 through 28 days postvaccination (Day 29) (Section 7.1.3).

Details on definition, evaluation, reporting periods and documentation are outlined in Section 7.

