The denominator for solicited AE tables comprises only those participants with at least one diary observation (i.e., any non-missing values but excluding "Not done/unknown"), at least one diary observation for a given symptom, or at least one diary observation for a given day, as applicable. *Note that an elevated in-clinic temperature assessment as part of 30-min post-vaccination vital signs does not count as a solicited AE, as vital signs data are summarized separately.*

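### The early-withdrawal visit schedule conflicts with the AE collection windows: unsolicited AEs are not asked about on Days 23-29, and diary review has no visit if Visit 3 was missed

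*Protocol*

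**What the plan says.** Protocol 5.2.9 has three rules for the Early Discontinuation/Withdrawal Visit:

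- "within 7 days after IP administration, the Visit 3 schedule will be followed"
- "from 7 days through 21 days after IP administration, the Visit 5 schedule will be followed"
- "after Day 22, the Visit 8 schedule will be followed"

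Footnote 13 to the Schedule of Events, in the Protocol and in SAP Figure 2, uses the same cut points.

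The three schedules differ in what they ask about:

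- **Visit 3 (5.2.3):** e-diary review and "Solicited AE, unsolicited AE, MAAE, SAE, and AESI evaluation". It is the only visit in the Schedule of Events at which the e-diary is collected and reviewed.
- **Visit 5 (5.2.5):** the same AE categories without solicited AEs, and no e-diary review.
- **Visit 8 (5.2.8):** "SAE, AESI, and MAAE evaluation" only, with concomitant medications limited to those linked to such events.

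The collection windows are set elsewhere. Solicited AEs are recorded to Day 8 (3.3.10, 8.7.2.1). Section 3.3.11 says that unsolicited AEs "will be collected from Day 1 through 28 days postvaccination (Day 29"), and 8.3.1 makes their incidence through Day 29 a primary safety endpoint. Section 5.3 collects all concomitant medications, names early discontinuation as a collection point, and narrows the scope only after Day 29.

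**The concern.** A withdrawal visit is usually the last chance to question a participant, so it should cover every category whose window is open and any assessment not yet done. In two bands the assigned schedule does not.

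On Days 23-29, AEs that are not medically attended and arise after the last AE contact are not asked about. Unasked events cannot be counted, so the effect on the unsolicited AE incidence is downward.

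From 7 to 21 days after dosing, a participant who never completed Visit 3 has no scheduled visit for the staff review of the diary and the investigator's severity and causality assessment that 3.3.10 requires. The direction of any effect here is less clear. SAP 6.3 counts an event whose only occurrence lacks a severity as severe, and one whose only occurrence lacks a relationship as related. The solicited results for such participants could therefore rest on imputation instead of assessment.

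At exactly 7 days, sites could follow different schedules for identical cases.

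**Working it through.** This is a comparison of texts. No sample-size, power or alpha figure depends on it.

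**Step 1. Put the rules on one scale.** Under SAP 6.3, Study Day = days after dosing + 1. The first rule then covers Days 1-8, the second Days 8-22, and the third Day 23 onward.

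**Step 2. Compare windows with schedules.**

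| Study day | Days after dosing | Schedule | Solicited AEs due / on schedule | Unsolicited AEs due / on schedule |
|---|---|---|---|---|
| 1-7 | 0-6 | Visit 3 | yes / yes | yes / yes |
| 8 | 7 | Visit 3 and Visit 5 | yes / Visit 3 yes, Visit 5 no | yes / yes |
| 9-22 | 8-21 | Visit 5 | closed / no | yes / yes |
| 23-29 | 22-28 | Visit 8 | closed / no | **yes / no** |
| 30 onward | 29 onward | Visit 8 | closed / no | closed / no |

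**Step 3. Days 23-29.** On all 7 days the unsolicited window is open and the schedule omits it. All concomitant medications are also still due under 5.3, and Visit 8 does not collect them. The unasked interval runs from the last AE contact to withdrawal:

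- If Visit 5 took place (window Day 21-25), the interval is at most 29 - 21 = 8 days.
- If Visit 5 was missed and Visit 4 (window Day 14-18) was the last contact, it is 23 - 18 = 5 to 29 - 14 = 15 days.
- If the Day 29 call (window Day 28-30) came before withdrawal, little or nothing is lost.

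**Step 4. Days 8-22.** Of these 15 days, solicited collection is open on one only, Day 8, which also meets the Visit 3 rule. On Days 9-22 what may be outstanding is the diary review and investigator assessment, and only for someone without a completed Visit 3. The Visit 3 window is Day 7-11, so this means a participant leaving on Days 8-11 before attending, or later after missing it. Under SAP 5.9, redness and swelling are categorised from the recorded diameter, so the missing investigator grade matters for the other solicited reactions. Causality is outstanding for all of them.

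**Step 5. Scale.** The documents give no withdrawal rate by day, and the 10% non-evaluable assumption is not one. As a conversion only, each 0.1% of participants withdrawing in a band is 3150 x 0.001 = 3.15 people, of whom six sevenths (2.7) are vaccinees.

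As a bound on the safety database, the plan's own figure reproduces: 1 - (1 - 0.001)^2700 = 0.9329, the stated 93.3%. Suppose 1% of vaccinees (27) contributed nothing: 1 - 0.999^2673 = 0.9310. For 5% (135): 1 - 0.999^2565 = 0.9232. Both percentages are assumptions, and both overstate the loss, because these participants still contribute data outside the gap.

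**The case against.** The strongest reply is that other provisions already protect these data:

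- Protocol 4.3.1, 4.3.2 and 4.3.4 ask for AE follow-up of every withdrawn participant.
- Section 7.2 records any AE reported in answer to an open question.
- Section 5.2.10 allows almost any procedure at an unscheduled visit.
- Sections 3.3.11 and 5.3 set their windows without excepting withdrawals.

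A careful site might therefore ask anyway. That is fair, but none of these puts the missing items on the visit. Section 4.3.3 refers back to the Early Withdrawal Visit as the protocol outlines it, unscheduled procedures are optional, and for medications 5.3 and the Visit 8 list contradict each other.

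The reply is stronger on solicited AEs. A reader might infer that these events are lost for anyone leaving 7 to 21 days after dosing, and that such participants leave the denominator. The documents do not support this. Collection closes at Day 8, and anyone who completed Visit 3 on or after Day 8 has had the full record reviewed. SAP 9.2.2 states: "The denominator for solicited AE tables comprises only those participants with at least one diary observation". One recorded value therefore keeps a participant in the overall solicited denominator. Reactions continuing past 7 days are recorded as unsolicited AEs (7.1.2.1), which Visit 5 collects, and solicited events that are serious or medically attended are also recorded as unsolicited (SAP 9.2.2).

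A reader might also infer that early withdrawers mostly leave because of reactions, so that a material share of severe reactions disappears. The documents give no reasons or rates to support that. An AE is a recorded reason for withdrawal (4.3.4), and AEs leading to discontinuation are listed (SAP 9.3.5).

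**Conclusion.** The point stands in three parts. The Days 23-29 branch is the firmest: a stated rule under-collects a primary safety endpoint and contradicts 3.3.11 and 5.3. Serious, special-interest and medically attended events are still captured there, so the loss is confined to AEs that were not medically attended and not volunteered. The second part is narrower: no scheduled diary review or investigator assessment when Visit 3 was not completed. The third is the double rule at exactly 7 days.

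The number affected cannot be computed and is probably small, and the bound above shows no threat to the size of the safety database. The plan should still be corrected, because the written schedule departs from windows that the protocol itself sets. The conclusion assumes that sites follow 5.2.9 as written. Sites that add the questions on their own initiative would reduce the loss, but not uniformly.

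**What to change.** Amend Protocol 5.2.9 and footnote 13 in both the Protocol Schedule of Events and SAP Figure 2:

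1. An early withdrawal visit through Day 29 also evaluates unsolicited AEs and all concomitant medications.
2. Any early withdrawal visit completes the e-diary review and solicited AE assessment if Visit 3 did not, including return of a backup paper diary where one was used.
3. The first two intervals no longer overlap at day 7.

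The text change is one paragraph and one footnote, repeated in the SAP. At the site it means a few extra questions at a visit that already takes place, with no new visit or sample. The real cost is a formal amendment with IRB approval (Protocol 12.2) at up to 50 sites.

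SAP 5.1.2 and 5.6 already describe some study conduct in the past tense, so an amendment may reach few of these visits. In that case, count the withdrawals in each band that lack the assessments and report them by treatment group with the safety results. That needs no amendment.

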5.2.10 Unscheduled Visits

Any study procedure, excluding vaccination, may be conducted at an Unscheduled Visit as needed and recorded on the Unscheduled Visit eCRF. Examples include repeat specimen collection and additional safety follow-up for an SAE/AESI/MAAE/AE.

5.3 **Prior and Concomitant Medications**

At the Screening Visit, the details of prior and concomitant medication usage will be collected (through 30 days prior to screening, or 90 days for blood products, or six months prior to screening for systemic immunomodulatory or immunosuppressive medications). Concomitant medications will be collected at each on site visit or by phone interview (or early discontinuation/withdrawal) for all groups. The details of all concomitant medications including those associated with solicited AEs and unsolicited AEs will be collected. After Day 29 only concomitant medications associated with SAEs, AESI, and MAAEs will be collected through the end of the study.

5.3.1 Required Concomitant Medications

Not applicable.

5.4 **Procedures for Monitoring Participant Compliance**

All participants will be administered the IP by study staff. Compliance with study protocol and procedures will be monitored on an ongoing basis by study staff.

6 IMMUNOGENICITY ASSESSMENT

6.1 Immunogenicity Analysis

The immunogenicity analysis will be performed using a high-throughput *in vitro* infectivity assay developed by the sponsor for assessing titers of neutralizing antibodies against CHIKV in serum samples. The assay is based on using a modified version CHIKV that expresses luciferase (CHIKV-luc) and measures the reduction of luciferase activity in infected cultures of Vero cells following treatment of virus with test serum. Using the human SNA assay, antibody neutralization titers can be determined via characterization of reductions of luciferase activity in the presence of immune serum. The quantitation of reporter gene expression, a correlate of the level of virus infection of cells, is determined by detection of luciferase in assay wells using a micro-plate luminometer. The CHIKV neutralizing antibody titer 80 (NT₈₀) is the reciprocal of the serum dilution that provides 80% protection of Vero cells from CHIKV-luc infection or an 80% reduction of luciferase activity compared to virus only control.

For the statistical analysis of the anti-CHIKV SNA titers results obtained from sample analysis refer to Section 8.6.

